3.3 Secondary Endpoints

Secondary endpoints include:

- 3.3.1 Efficacy of short-term nicotine transdermal patch administration in the treatment of CIPN in patients whose cancer is stable or in remission by assessing changes in the degree of pain-related functional interference measured by the BPI-SF interference score.
- 3.3.2 Nicotine transdermal patch safety and tolerability in non-smokers by assessing AEs characterized and graded according to CTCAE v5.0 and PROs related to nausea, dizziness, vomiting, minor skin irritations, and palpitations.

4 PATIENT SELECTION

4.1 Inclusion Criteria

A patient must meet all of the following inclusion criteria to be eligible to participate in the study.

4.1.1 Age ≥ 18

4.1.2 CIPN characteristics

4.1.2.1 Clinically diagnosed peripheral sensory neuropathy defined as:

4.1.2.1.1 Greater than Grade 1 peripheral sensory neuropathy using the CTCAE v5.0 grading scale

- **Grade 1** Asymptomatic
- **Grade 2** Moderate symptoms; limiting instrumental activities of daily living (ADL)
- **Grade 3** Severe symptoms; limiting self-care ADL
- **Grade 4** Life-threatening consequences; urgent intervention indicated

AND

4.1.2.2 Have a baseline CIPN PRO total sensory score ≥ 24.3 on a 19 to 76 scale using the EORTC QLQ-CIPN-20 questionnaire

AND

4.1.2.3 Have a CIPN-related neuropathic pain score ≥ 4 on a 0 to 10 scale using the Brief Pain Inventory-Short Form (BPI-SF) item 5

Note: Patients currently being treated for CIPN will not be excluded and are allowed to continue their treatment and current treatment dose while on study.

4.1.3 Will not have used any nicotine or tobacco products (eg, cigarettes, electronic cigarettes, smokeless tobacco, or other nicotine replacement therapies) within 14 days prior to study treatment start date

4.1.4 Eastern Cooperative Oncology Group (ECOG) performance status of 0, 1, or 2 (see [Appendix 1](#))

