1.3 Study Design

This study will test the efficacy of acute nicotine transdermal patch administration using an open-label, within-subjects clinical trial design with nicotine transdermal patch concentrations of 7 mg and 14 mg. Patients will be recruited via clinician referral and must not have used any nicotine or tobacco products (eg, cigarettes, electronic cigarettes, smokeless tobacco, or other nicotine replacement therapies) within the last 14 days prior to study treatment start date. Each treatment condition will have a duration of 14 days, with a washout period of at least 14 days in between conditions. Patients will be evaluated by the study team once per week during the treatment cycles (2 study visits per treatment cycle). Patients will be evaluated by the study team once during the washout period (1 study visit). Patients will also be evaluated at least once during the 30-day follow-up period (1 study visit). During study visits, patients will be evaluated by the study team for CIPN PROS, pain scale, and Adverse Events (AE). This evaluation schedule will provide complete clinical and research assessments related to pain and neuropathy at baseline, during treatment conditions, and post-treatment.

The primary outcome measure is the change in CIPN-related PRO as measured by the total sensory score of the European Organization for Research and Treatment of Cancer quality of life questionnaire (EORTC QLQ-CIPN-20). EORTC QLQ-CIPN-20 is a well-developed 20-item questionnaire, that provides valuable information on CIPN- related symptoms and functional limitations of patients exposed to potentially neurotoxic chemotherapeutic and/or neuroprotective agents ([17](#)). It has also been validated clinically by showing very significant association between QLQ-CIPN20 scores and the NIH Common Terminology Criteria for Adverse Events (CTCAE) grades for AEs associated with CIPN symptoms ($p<0.0001$), whereby patients with higher CTCAE grade had worse QLQ-CIPN20 scores ([18](#)).

The secondary outcome measures include the following items: 1) the change in average pain based on the well-validated Brief Pain Inventory-Short Form (BPI-SF) average pain severity item; and 2) evaluation of the safety and toxicity of nicotine transdermal patch administration in a population of non-smokers experiencing CIPN.

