The clinical trial will yield several important results. First, using an acute nicotine transdermal patch administration will determine both the potential efficacy and feasibility of using nicotine as a potential treatment for neuropathic pain associated with CIPN. Additionally, if nicotine appears to have a positive treatment effect, as defined by a ≥ 2.7 point decrease in patient’s total sensory score (baseline compared to treatment and post-treatment scores) of the QLQ-CIPN-20 questionnaire (eg, an improvement in the patients quality of life by one grade), future randomized clinical trials comparing nicotine to other commonly prescribed treatments, such as duloxetine, may be warranted. In addition, further studies of subtype receptor selective agents or of patient population subgroups (based on smoking history, gender, chemotherapeutic agents, or receptor expression level) can be designed.

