12 STUDY CALENDAR

Table 3. Study Caledar – Eligibility/Screening Through Washout Period

	Eligibility and Screening	Cycle 1 Treatment Condition 1 7mg Nicotine Transdermal Patch ^A			Washout Period No Nicotine Transdermal Patch ^B
	Within 14 Days	D1	D2	D8 ^C	
Informed Consent ^D	X				
Demographics	X				
Vital Signs (BP, HR) ^E	X	X		X	
Baseline Conditions/Symptoms	X				
Medical/Surgical History	X				
Exam ^F	X ^G			X	
Concurrent Medications ^H	X	X		X	
Urine Pregnancy Test	X				
Serum Nicotine Level	X			X	
Assessment of AEs		X		X	
BPI-SF	X			X	
QLQ-CIPN 20	X			X	
PGIC Neuropathy (upper and lower)				X	
AE Assessment Phone Call			X		X ^I

Table 3 Footnotes:

- A. Each Treatment Condition Cycle is 14 days.
- B. Washout period may occur for \geq 14 days and up to 21 days after the removal of the nicotine transdermal patch on Cycle 1
- C. Cycle 1, Day 8 study visit may occur within 5 days.
- D. If registration is delayed to more than 14 days after the informed consent form is signed, a new signed consent form is not required unless the IRB has approved a newer version.
- E. Include ECOG performance status.
- F. Exam will also include a neurological exam: sensory, motor, reflex, Romberg, and gait.
- G. If the neurological exam cannot be completed on the day of screening, it can be completed on Cycle 1, Day 1, but does not need to be completed for both screening and Cycle, Day 1.
- H. Include over-the-counter medications.
- I. The AE assessment phone call during the washout period will include notation of the date the last nicotine transdermal patch was removed in Cycle 1.

Table 4. Study Calendar – Treatment Condition 2 Through the 90-Day Follow-up Period

	Cycle 2 Treatment Condition 2 14mg Nicotine Transdermal Patch ⁰			30-Day Follow-up Period		90-Day Follow-up Period ^B
	D1 ^C	D2	D8 ^D	D1	D8 - D15 ^E	
Vital Signs (BP, HR) ^F	X		X		X	
Exam ^G	X		X		X	
Concurrent Medications ^H	X		X		X	
Serum Nicotine Level	X ^I		X		X	
Assessment of AEs	X ^I		X		X	
BPI-SF	X ^I		X		X	
PGIC Neuropathy (upper and lower)	X ^I		X		X	
QLQ-CIPN 20	X ^I		X		X	
AE Assessment Phone Call		X		X ^J		
Follow-up Phone Call						X ^{B, K}

Table 4 Footnotes:

- A. Each Treatment Condition Cycle is 14 days.
- B. The 90-day follow-up period will begin at the end of Cycle 2, after the last nicotine transdermal patch is removed. The 90-day follow-up phone call may occur \pm 14 days.

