- C. Cycle 2, Day 1 may occur \geq 14 days and up to 21 days after the removal of the nicotine transdermal patch in Cycle 1.
- D. Cycle 2, Day 8 study visit may occur within 5 days.
- E. 30-day follow-up, Day 8 - Day 15 study visit may occur within 7 days.
- F. Include ECOG performance status.
- G. Exam will also include a neurological exam: sensory, motor, reflex, Romberg, and gait.
- H. Include over-the-counter medications.
- I. Must occur before 14 mg nicotine transdermal patch is administered.
- J. 30-day follow-up, the AE assessment phone call will include notation of the date the last nicotine transdermal patch was removed in Cycle 2.
- K. 90-day follow-up, the phone call will assess whether patients have continued to use the nicotine transdermal patch to lessen their CIPN symptoms and if they have developed a dependence to nicotine in any form (eg, cigarettes, electronic cigarettes, smokeless tobacco, or other nicotine-containing products).

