13.1 Sample Size and Accrual

Using the 19-76 numerical scale for QLQ-CIPN220, a minimum decrease of 2.7 points (range of 2.7 – 5.6 points) would be required to improve the patient's quality of life by one grade (grade 2 to grade 1). A sample size of 47 would provide a power of at least 95% to detect a minimum change of 2.7 EORTC QLQ-CIPN20 scale points, assuming a moderately sized effect (ie, effect size 0.54) and 5% level of significance. Assuming 10% dropout or non-compliance, this will bring the total size to 52 patients. Recruitment ends when the required number of evaluable patients to complete the study is reached. A patient is evaluable if pain scores are available for the patient with each dose level. This still might have missing values due to non-compliance. All of the patients will be included in the final analysis and subjects with missing values will be included based on imputation-based method provided the amount of missing values is not excessive. If final data contains patients with more than 50% missing observations, we will use a pattern mixture model for imputation of missing data followed by longitudinal data.

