13.2 Statistical Analysis

13.2.1 Analysis of Primary Endpoint

The primary endpoint of the study is the decrease in neuropathic pain symptoms for CIPN patients using a short-term nicotine transdermal patch. CIPN PROs will be measured using the EORTC QLQ-CIPN20 sensory subscale score. The QLQ-CIPN20 numerical score has a range of 19-76, in which lower scores indicate less symptoms and a better quality of life. Patient QLQ-CIPN20 scores at baseline, during treatments, and post-treatment will be analyzed by a one-sided test of the hypothesis using a matched paired t-test using 5% level of significance. Data will be tested for compliance with normality assumption and simple transformations would be used if required to restore normality of the data.

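### In Table 3 the only QLQ-CIPN20 score before the first patch is the screening score used to select patients; as baseline it lets regression to the mean count as improvement, and Section 1.3 and Table 3 need reconciling

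*Combined protocol and SAP*

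**What the plan says.** **Selection.** Section 4.1.2.2 admits patients who "Have a baseline CIPN PRO total sensory score ≥ 24.3 on a 19 to 76 scale using the EORTC QLQ-CIPN-20 questionnaire". Section 4.1.2.3 adds a score of at least 4 on BPI-SF item 5.

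**Schedule.** Table 3 marks QLQ-CIPN20 and BPI-SF at screening and Cycle 1 Day 8. Cycle 1 Day 1 has vital signs, concurrent medications and adverse events, but no questionnaire. For Cycle 2, Table 4 marks both questionnaires on Day 1, and footnote I says: "Must occur before 14 mg nicotine transdermal patch is administered". Section 13.4.2 counts five questionnaire points, which fits Tables 3 and 4 exactly: screening, Cycle 1 Day 8, Cycle 2 Day 1, Cycle 2 Day 8 and follow-up. For blood samples, Section 11.2.1 treats eligibility and baseline as one time point.

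**Section 1.3.** It says "Patients will be evaluated by the study team once per week during the treatment cycles (2 study visits per treatment cycle" and "During study visits, patients will be evaluated by the study team for CIPN PROS, pain scale, and Adverse Events (AE". It also gives one study visit in the washout, where Table 3 shows only a phone call.

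**Analysis.** Section 1.3 describes the contrast as "baseline compared to treatment and post-treatment scores". Section 13.2.1 says "Patient QLQ-CIPN20 scores at baseline, during treatments, and post-treatment will be analyzed by a one-sided test of the hypothesis", using a matched paired t-test at 5%. It does not say which score is the baseline. The design is open-label, and every patient receives both active doses.

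**The concern.** A questionnaire score is part true level and part short-term fluctuation. Patients admitted because one score reached a cutoff have, on average, some upward fluctuation in that score. At the next measurement the fluctuation is not repeated, so the mean falls even if the patch does nothing. The paired test looks for exactly this fall, and without an untreated control nothing subtracts it.

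At stake is the meaning of the 5% level. Section 1.3 says a positive effect may warrant randomized trials against other treatments, so a false positive has a cost later on.

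Separately, Section 1.3 and Table 3 disagree. Apart from the Day 2 phone call, the Cycle 1 contacts in Table 3 are Day 1 and Day 8. Two study visits with patient-reported outcomes therefore imply a Day 1 questionnaire that Table 3 omits, and Section 1.3 does not say whether it would precede the patch.

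**Working it through.** **The plan's own figure.** Section 13.1 (Sample Size and Accrual) gives n = 47, at least 95% power and a 2.7-point change, "assuming a moderately sized effect (ie, effect size 0.54) and 5% level of significance". The implied SD of change is 2.7 / 0.54 = 5.0. With the noncentral t, power at n = 47 is 95.2% two-sided and 97.7% one-sided (the test in Section 13.2.1). The stated figure is reproduced.

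**Inputs.** From the documents: cutoff 24.3, n = 47, change SD 5.0, one-sided 5%. Assumed, because the documents do not give them: pool mean μ, test-retest correlation r from 0.5 to 0.9, normal scores, no drug effect. The means 29.9 and 33.6 are the Table 2 values for Grades 2 and 3, and 31.75 is their midpoint.

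**Formulas.**
- Score SD: s = 5 / √(2(1 − r)), which keeps the change SD at 5.0 before selection.
- Standardised cutoff: a = (24.3 − μ) / s, and λ = φ(a) / (1 − Φ(a)).
- Expected spurious fall: (1 − r) · s · λ.
- Variance of change after selection: (1 − r)² · s²(1 + aλ − λ²) + s²(1 − r²).

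**One case in full, μ = 29.9 and r = 0.7.**
- s = 5 / √0.6 = 6.45; a = −5.6 / 6.45 = −0.87; λ = 0.274 / 0.807 = 0.339.
- Spurious fall: 0.3 × 6.45 × 0.339 = 0.66 points.
- SD of change after selection: 4.84.
- Noncentrality: 0.657 × √47 / 4.84 = 0.93. Against the one-sided critical value 1.679 on 46 df, the rejection rate is about 23%.

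**All cases.** Ranges are over r = 0.5 to 0.9. Rates come from 20,000 simulated trials per cell, and the formula agrees to about one percentage point.

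| Pool mean | Share passing cutoff | Spurious fall (points) | False-positive rate |
|---|---|---|---|
| 27 | 60–71% | 0.73–1.22 | 26–54% |
| 29.9 | 69–87% | 0.57–0.66 | 19–24% |
| 31.75 | 75–93% | 0.35–0.49 | 12–16% |
| 33.6 | 80–97% | 0.18–0.40 | 8–14% |
| 40 | 92% or more | 0.01–0.18 | 5–9% |

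The mean of 27 lies below the Table 2 value for Grade 2, although entry requires Grade 2 or worse. It is shown as an unfavourable case.

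**Skewed scores.** With right-skewed whole-number scores confined to 19–76, the rates are 27–36% at 29.9, 14–25% at 31.75, 9–16% at 33.6 and 5–7% at 40, with falls of 0.01 to 0.90 points.

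**Reaching 2.7 points.** The chance of a mean fall of at least 2.7 with no drug effect is at most about 0.3% for means of 29.9 and above (0.5% with skewed scores), and 0.3–1.5% at mean 27. Read patient by patient for means 29.9 to 33.6, 30–34% of patients would show such a fall, against about 29% without selection (2.7 / 5.0 = 0.54 SD, upper tail 0.29).

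**With a separate Day 1 pre-patch baseline.** If screening and Day 1 errors are independent, the rate is 4.6–5.4% in every cell. For means 29.9 to 33.6 it is about 6–8% at error correlation 0.25, 6–11% at 0.5 and 7–18% at 0.8. Re-applying the 24.3 cutoff to the Day 1 score would bring back 7–17%.

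**The case against.** **The efficacy criterion is hardly touched.** Section 3.2 defines efficacy as a fall of at least 2.7 points. A reader might infer that this artefact could get an inactive patch past that criterion. The figures above do not support that for the mean change. But Section 13.2.1 tests only for a decrease and does not require 2.7 points, so the significance test is still exposed.

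**The plan does not say that screening is the analysis baseline.** This is true, and the inflation is conditional on it. However, Section 4.1.2.2 uses that word for the screening score, Section 13.4.2 counts five points that leave no room for another, and Table 3 offers no other pre-patch score.

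**The cutoff may seldom bind.** It equals the Grade 1 value in Table 2, while entry requires more than Grade 1 plus pain of at least 4. If most of the pool scores well above 24.3, the excess is small (5–9% at mean 40). This stands, and the documents cannot settle it.

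**BPI-SF.** A reader might infer that both BPI-SF analyses are biased in the same way. The documents do not support that. Only item 5 is used for entry, and they do not say which item that is. Average pain is exposed only if item 5 is the average-pain item; the interference score selects no one and is affected at most indirectly.

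**An off-patch score already exists at Cycle 2 Day 1.** It is not used for selection, but it follows the 7 mg cycle and the plan gives it no baseline role.

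**Section 1.3 is a background summary.** The tables and Section 13.4.2 agree with each other, so the conflict may be loose wording. The passages still need to be reconciled.

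**Conclusion.** The point holds as a cheap improvement, not as a flaw that invalidates the trial. If the screening score serves as baseline, the one-sided test rejects more often than 5% with an inactive patch. The direction is certain; the size is not. It rests on an assumed pool mean, test-retest correlation and score distribution. Under normal scores the rate runs from 5–9% where nearly all patients clear the cutoff to 19–24% at the Grade 2 mean, with about 54% in the least favourable case examined; skewed scores raise the figures for means 29.9 to 33.6. The spurious fall is about 0 to 0.7 points for means 29.9 to 40 under the normal model.

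A reader might also infer that a Day 1 baseline would make the uncontrolled comparison sound. It would not: open-label placebo response inflates the same test and is unaffected.

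**What to change.** - **Table 3:** add QLQ-CIPN20 and BPI-SF at Cycle 1 Day 1, before the first patch, as Table 4 footnote I does for Cycle 2.
- **Section 4.1.2.2:** replace the word baseline with screening. State that the questionnaire cutoffs apply to the screening scores only, and reconcile this with Section 6.1, which expects eligibility to be maintained until treatment starts.
- **Section 13.2:** define baseline as the Cycle 1 Day 1 pre-patch score, and keep the planned contrast with treatment and post-treatment scores.
- **Section 13.4.2:** count Day 1 in place of screening, so that three of five stands.
- **Missed Day 1 score:** handle it by the imputation in Section 13.1 (Sample Size and Accrual), not by substituting the screening score.
- **Section 1.3 and Table 3:** reconcile the Cycle 1 visits and the washout contact, which is a study visit in one place and a phone call in the other.

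The cost is two short questionnaires at a visit that already takes place; Table 3 footnote G already allows for assessment that day: "If the neurological exam cannot be completed on the day of screening, it can be completed on Cycle 1, Day 1". Sample size and planned power do not change. The downside is that a patient may now lack a baseline, which cannot happen while eligibility depends on that score. The protection is full only if screening and Day 1 errors are independent.

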1 BACKGROUND

1.1 Introduction

Chemotherapy-induced peripheral neuropathy (CIPN) is a common side effect associated with the taxanes and platinum-based compounds, drugs commonly used for the treatment of breast, lung, and ovarian cancer. CIPN results from damage to, or dysfunction of, the peripheral motor, sensory, and autonomic nerves and manifests with a variety of symptoms including mechanical and cold allodynia, numbness and tingling, loss of proprioception, and long-lasting burning pain (1-4). CIPN affects quality of life, and can often result in chemotherapy dose reductions and early treatment discontinuation (5).

Depending on the specific chemotherapy regimen used, the duration of exposure, and method of CIPN assessment, approximately 30% to 70% of multiple-agent, chemotherapy-treated cancer patients are diagnosed with CIPN (6-8). Current CIPN treatment options include duloxetine, tricyclic antidepressants, gabapentin, and topical applications (eg, baclofen and ketamine) (5). However, treatment options to manage CIPN are not consistently effective for the majority of patients. Thus, there is a critical need to identify new agents that can manage the pain associated with CIPN.

This clinical trial is designed to determine if nicotine transdermal patch use can suppress the pain associated with CIPN. Demonstrating that nicotine can suppress such pain would be highly significant on 3 fronts. First, by relieving CIPN-associated pain, suboptimal chemotherapeutic dosing schemes might be adjusted upwards, increasing the probability of effective treatment of the cancer. Second, the use of an FDA-approved, over-the-counter drug with a relatively safe short-term use profile would greatly accelerate the clinical development of this pain management strategy. Third, a demonstration that nicotine can manage the pain associated with CIPN would stimulate the development of targeted agents that interact with subtypes of nicotinic acetylcholine receptors (nAChRs) and which might act with fewer side effects.

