4.1.5 Not currently receiving any chemotherapy

4.1.6 Have previously received platinum- and/or taxane-based chemotherapy treatments and have persistent pain at least 3 months after completion of treatments.

- 4.1.7 Willing and able to comply with study procedures and visit schedule.
- 4.1.8 Willing to abstain from all tobacco/nicotine product use during study treatment and 30-day follow-up period.
- 4.1.9 Ability to self-apply or have the patch applied at home daily.
- 4.1.10 Ability to understand and the willingness to sign a written informed consent document

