4.2.3 Current or prior pheochromocytoma

4.2.4 History of or active or clinically significant cardiac disease including any of the following:

- Unstable angina (eg, anginal symptoms at rest) or onset of angina within 3 months prior to initiating study treatment
- Myocardial infarction diagnosed within 6 months prior to initiating study treatment
- Cardiac arrhythmias requiring anti-arrhythmic therapy other than beta blockers

4.2.5 New York Heart Association (NYHA) class III or IV congestive heart failure (see [Appendix 2](#))

4.2.6 Poorly controlled high or low blood pressure defined as:

- SBP \geq 140; DBP \geq 90

- SBP ≤ 90; DBP ≤ 60

4.2.7 Regular use of the following medications:

- Varenicline
- Bupropion (ie, bupropion hydrochloride sustained release)

4.2.8 Women will be excluded if they are breastfeeding or are pregnant (by urinalysis) within 14 days prior to the start of nicotine transdermal patch administration.

4.2.9 Medical, psychological, or social condition that, in the opinion of the investigator, may increase the patient's risk or limit the patient's adherence with study requirements

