6.2 Investigational Agent Administration

6.2.1 Nicotine Transdermal Patch Administration and Treatment Schedule:

- Each patient will complete two 14-day treatment conditions, one each for 7 mg and 14 mg nicotine transdermal patch administration with a washout period in between (\geq 14 days and up to 21 days).
- Nicotine transdermal patch administration will begin on Cycle 1, Day 1 (7mg) and Cycle 2, Day 1 (14mg).
- Nicotine transdermal patches will be applied once daily for 14 consecutive days.
- Nicotine transdermal patches will be removed for at least 14 days and up to 21 days at the end of Cycle 1, Day 14.
- Patients will be instructed as follows:
 - Apply the nicotine transdermal patch to dry, clean, hairless skin
 - Patients should apply and remove the nicotine transdermal patch at the same time everyday
 - Patients should wear the nicotine transdermal patch for at least 16 hours per day.

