13 STATISTICAL CONSIDERATIONS

13.1 Study Design

This is a phase 2 study that will test the efficacy of acute nicotine transdermal patch administration using an open-label, crossover within-subjects clinical trial design with nicotine transdermal patch concentrations of 7 mg and 14 mg. Patients will be evaluated for nicotine-associated toxicity and undergo assessments of pain and neuropathy administered by the study team, which will provide subjective and clinical measurements at baseline, during treatment conditions, and post-treatment. The primary endpoint is to assess the efficacy of short-term nicotine transdermal patch administration in the treatment of CIPN in patients whose cancer is stable or in remission by assessing decreases in neuropathic pain symptoms measured by the total sensory score of the EORTC QLQ-CIPN-20.

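### Patients already on CIPN treatment may enter without any period of unchanged treatment before the baseline score, so the effect of a recent change in that treatment is attributed to nicotine

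*Combined protocol and SAP*

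**What the plan says.** The Note under the CIPN inclusion criteria (section 4.1.2) reads: "Patients currently being treated for CIPN will not be excluded and are allowed to continue their treatment and current treatment dose while on study". Section 1.1 names the treatments in view: "Current CIPN treatment options include duloxetine, tricyclic antidepressants, gabapentin, and topical applications".

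The other rules that might bear on this do not address the timing of that treatment:

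- Section 4.1.6 requires that patients "have persistent pain at least 3 months after completion of treatments". That clock runs from the end of chemotherapy.
- Section 4.2.7 excludes "Regular use of the following medications", and lists only varenicline and bupropion.
- Section 6.3 deals with nicotine side effects and anti-emetics.
- The study calendar (section 12) records concurrent medications at screening and at visits, with the footnote "Include over-the-counter medications". Efficacy evaluability (13.4.2) and the analyses (13.2.1, 13.2.2) make no use of that record.

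Section 13.1 describes an "open-label, crossover within-subjects clinical trial design with nicotine transdermal patch concentrations of 7 mg and 14 mg". Section 6.2.1 gives every patient 7 mg first and 14 mg second. On the primary analysis, section 13.2.1 says: "Patient QLQ-CIPN20 scores at baseline, during treatments, and post-treatment will be analyzed by a one-sided test of the hypothesis using a matched paired t-test".

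**The concern.** A patient who began or increased another CIPN drug a few days before screening meets every criterion and follows the plan exactly by staying on that dose. If the drug's effect is still building, the score falls after baseline for a reason unrelated to the patch. No placebo or untreated group shows how large that fall would have been, so the paired difference assigns all of it to nicotine. Because the dose order is fixed, an improvement that continues through both cycles could also look like a dose response.

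The reverse is possible too. A patient who recently reduced or stopped a CIPN drug may worsen after baseline, which would hide a real benefit.

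At stake is the decision in section 1.3 on whether randomised trials against other treatments are warranted. In an uncontrolled design, stability before baseline is one of the few protections available, and it cannot be added once patients are enrolled.

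**Working it through.** **1. The plan's own sample size.** Inputs from the sample size paragraph in section 13: n = 47, effect size 0.54, 5% level, power at least 95%. For a paired t-test the noncentrality is 0.54 × √47 = 3.70 with 46 degrees of freedom. Power is 95.2% two-sided, and 47 is the smallest n that reaches 95%. For the one-sided test named in 13.2.1, power is 97.7%. The stated figure reproduces.

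**2. Implied SD of the change.** 2.7 / 0.54 = 5.0 points.

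**3. Mean fall that reaches significance.** The one-sided 5% critical value of t with 46 degrees of freedom is 1.679, so the fall is 1.679 × 5.0 / √47 = 1.22 points. That is less than half of the 2.7-point target.

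**4. Time for a background effect to act.** Screening is within 14 days before Cycle 1, each cycle lasts 14 days, washout 14 to 21 days, and the follow-up visit is on Day 8 to 15. From screening to follow-up this is 0 + 14 + 14 + 14 + 8 = 50 days to 14 + 14 + 21 + 14 + 15 = 78 days, before visit windows. The first on-treatment score (Cycle 1 Day 8) comes about 1 to 3 weeks after screening.

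**5. Illustration.** Assume the true nicotine effect is zero and a fraction f of patients improve by d points because of another drug. The documents give neither f nor d. The values 2.7 and 5.6 are the ends of the one-grade range in section 10.1; 1 point is a smaller case.

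- Spurious mean decrease: m = f × d
- SD: s = √(25 + f(1 − f)d²)
- Chance of significance: P(T > 1.679), where T is noncentral t with 46 degrees of freedom and noncentrality m√47 / s
- Chance that the observed mean decrease reaches 2.7: 1 − Φ((2.7 − m)√47 / s)

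Example with f = 20%, d = 2.7: m = 0.54; s = √(25 + 0.16 × 7.29) = 5.115; noncentrality = 0.54 × 6.856 / 5.115 = 0.724; chance of significance 17.6%. For the threshold, (2.7 − 0.54) × 6.856 / 5.115 = 2.895, a chance of 0.19%.

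| d (points) | f | m | Significant (nominal 5%) | Mean decrease reaches 2.7 |
|---|---|---|---|---|
| 1 | 10% | 0.10 | 6.6% | 0.02% |
| 1 | 20% | 0.20 | 8.4% | 0.03% |
| 1 | 30% | 0.30 | 10.7% | 0.05% |
| 2.7 | 10% | 0.27 | 9.9% | 0.05% |
| 2.7 | 20% | 0.54 | 17.6% | 0.2% |
| 2.7 | 30% | 0.81 | 28.0% | 0.6% |
| 5.6 | 10% | 0.56 | 17.7% | 0.3% |
| 5.6 | 20% | 1.12 | 39.6% | 2.4% |
| 5.6 | 30% | 1.68 | 64.6% | 10.7% |

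Simulation of 200,000 trials gave 17.6% for f = 20%, d = 2.7 and 39.3% for f = 20%, d = 5.6.

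**The case against.** **Size.** A reader might infer from the lower rows of the table that the trial's error rate is 40% or 65%. The documents do not support that. Those figures need 20% to 30% of patients to gain 5.6 points on average from another drug, while section 1.1 says existing options are not consistently effective for most patients. At 1 point the rate is only 7% to 11%. This stands, and the percentages are illustrative.

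**The 2.7-point threshold.** Sections 1.3 and 3.2 define efficacy as a decrease of at least 2.7 points. If that applies to the observed mean, spurious success becomes rare in most cases. This also stands, but 13.2.1 names only the t-test, and 3.2 can be read per patient, so the plan does not settle which rule decides.

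**Direction.** A reader might infer that the bias always favours nicotine. It does not: patients with a recent reduction or stop are equally eligible.

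**On-study dose.** The Note can be read as expecting a constant dose after entry. It is worded as a permission, and even on the strict reading it does not reach changes made before baseline.

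**Scores off the patch.** QLQ-CIPN20 is repeated after washout, before the 14 mg patch, and a lasting background gain could show there. That is a useful check, but the named test does not commit to using it.

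**Purpose.** This is a proof-of-principle study, and placebo response and regression to the mean remain whatever is done here. That limits what the fix achieves; it does not remove the reason for a cheap one.

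**Conclusion.** The point holds as a gap in eligibility and analysis. Treated patients may enter, no period of unchanged treatment before the baseline score is required, and the uncontrolled paired test cannot separate the effect of a recent treatment change from that of the patch. The bias can go either way, and an ongoing improvement could resemble a dose response under the fixed order.

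Its size cannot be derived from the documents. With zero nicotine effect, n = 47, SD 5.0 and 10% to 30% of patients improving by 1 to 5.6 points because of another drug, the false-positive rate lies between about 7% and 65% on significance alone, and between about 0.02% and 11% if the mean decrease must also reach 2.7 points. Neither the fraction nor the improvement is given in the plan, so these are ranges under assumption and not an estimate for this trial. The part of section 9 before 9.1.9 is not in the public text and could not be checked. The change is worth making because it is cheap.

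**What to change.** 1. Add to the Note in 4.1.2 an entry condition that any treatment for CIPN or neuropathic pain has been unchanged for a pre-specified period before the screening QLQ-CIPN20 and BPI-SF. The clinical team sets the length. Allow re-screening of patients who do not yet meet it. The condition concerns stability only and does not direct what treatment a patient receives.
2. Record the start date and date of last change for each such treatment, alongside the concurrent medications already collected.
3. Pre-specify in 13.2.1 a sensitivity analysis of the primary endpoint that excludes patients whose CIPN treatment changed within that period before baseline, and scores taken after any on-study change.

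The cost is one sentence and one checklist line for eligibility, two dates per drug, one further analysis, and a short entry delay for recently changed patients. The planned 47 evaluable and 52 total patients are unaffected. The fix removes this source of bias only; placebo response and regression to the mean would remain.
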